### 3.2 Exclusion Criteria

- 3.2.1 Patients who develop acute GVHD prior to start of study drug
- 3.2.2 Patients at very high risk for relapse post HCT as defined by very high disease risk index
- 3.2.3 Patients participating in a clinical trial where prevention of GVHD is the primary endpoint
- 3.2.4 Uncontrolled active infection (i.e., progressive symptoms related to infection despite treatment or persistently positive microbiological cultures despite treatment or any other evidence of severe sepsis)
- 3.2.5 Patients who are pregnant
- 3.2.6 Patients on dialysis within 7 days of enrollment
- 3.2.7 Patients requiring ventilator support or oxygen supplementation exceeding 40% FiO2 within 14 days of enrollment.
- 3.2.8 Patients receiving investigational agent within 30 days of enrollment. However, the Principal Investigator (PI) may approve prior use of an investigational agent if the agent is not expected to interfere with the safety or the efficacy of alpha-1-antitrypsin
- 3.2.9 History of allergic reaction to alpha-1-antitrypsin

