## **3.0 PATIENT ELIGIBILITY**

Subjects must meet all of the inclusion and none of the exclusion criteria to be eligible to participate in the study. Study treatment may not begin until a subject is enrolled.

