#### 8.1.1 Contraindications

Patients who have had an allergic reaction to alpha-1-antitrypsin

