#### 8.1.2 Special Warnings and Precautions for Use

Severe hypersensitivity and anaphylactic reactions may occur in IgA deficient patients with antibodies against IgA and in patients with a history of hypersensitivity to other Alpha1-AT products. These reactions are not expected in this study because of the immunosuppressive nature of the transplant procedure.

May carry a risk of transmitting infectious agents such as viruses, the variant Creutzfeldt-Jakob disease (vCJD) and theoretically, the Creutzfeldt-Jakob disease (CJD) agent.

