## 9.0 DRUG INFORMATION

### 9.1 ALPHA-1-ANTITRYPsin (AAT, AAT, A1PI)

- Commercial names for the drug: GLASSIA®
- Classification - type of agent: Human Alpha-1 Proteinase Inhibitor
- Description: AAT (Glassia) is supplied as contains a single use vial containing approximately 1 gram of functional Alpha1-PI in 50 mL of solution and a sterile filter needle
- Mode of action: The mode of action of AAT in graft-versus-host disease is not well understood, but appears to be related to its anti-inflammatory, anti-apoptotic and immunomodulatory properties.
- Pharmacokinetics: A prospective, open-label, uncontrolled multicenter pharmacokinetic trial was conducted in 7 females and 11 males with congenital Alpha-1 antitrypsin deficiency, ranging in age from 40 to 69 years. Subjects received a single dose of GLASSIA either 30 mg/kg, 60 mg/kg or 120 mg/kg. Blood samples for pharmacokinetic study were taken prior to and within 5 minutes of completion of the infusion, and then at 1 hour, 6 hours, 12 hours, 24 hours, 3 days and 7 days. The mean results for pharmacokinetic parameters in the 60 mg/kg dosage group are shown in the Table. The pharmacokinetics of GLASSIA were linear over the dose range of 30-120 mg/kg.

Pharmacokinetic Parameter	60 mg/kg Dose Group
Terminal Half-Life (h) *	111 ± 33
Area under the curve 0-168 hrs (mg·h·mL)	89 ± 10
Clearance (mL/h/kg)	0.68 ± 0.1
Volume of Distribution (L)	3.2 ± 0.3

- Adverse reactions: The most common adverse reactions (>0.5% of infusions) in clinical trials were headache and upper respiratory infection.

GLASSIA may contain trace amounts of IgA. Patients with known antibodies to IgA, which can be present in patients with selective or severe IgA deficiency, have a greater risk of developing severe hypersensitivity and anaphylactic reactions.

Because this product is made from human plasma, it may carry a risk of transmitting

infectious agents, such as viruses, the variant Creutzfeldt-Jakob disease (vCJD) and theoretically, the Creutzfeldt-Jakob disease (CJD) agent. This also applies to unknown or emerging viruses and other pathogens. The risk of transmitting an infectious agent has been minimized by screening plasma donors for prior exposure to certain viruses, by testing for the presence of certain current virus infections and by inactivating and removing certain viruses during the manufacturing process. Despite these measures, such products may still potentially transmit human pathogenic agents.

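### A patient with known antibodies to IgA and no prior reaction to AAT is eligible as written, although 8.1.2 and 9.1 warn of severe hypersensitivity and anaphylaxis in this group

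*Combined protocol and SAP*

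**What the plan says.** Section 3.0 makes the two criteria lists decisive: "Subjects must meet all of the inclusion and none of the exclusion criteria to be eligible to participate in the study". Of the nine exclusions in 3.2, one concerns allergy: "History of allergic reaction to alpha-1-antitrypsin" (3.2.9, repeated as synopsis exclusion 9). Section 8.1.1 lists one contraindication, again prior AAT allergy: "Patients who have had an allergic reaction to alpha-1-antitrypsin".

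IgA appears in two places. In 9.1, under adverse reactions: "GLASSIA may contain trace amounts of IgA", followed by "Patients with known antibodies to IgA, which can be present in patients with selective or severe IgA deficiency, have a greater risk" of severe hypersensitivity and anaphylaxis. In 8.1.2: "Severe hypersensitivity and anaphylactic reactions may occur in IgA deficient patients with antibodies against IgA and in patients with a history of hypersensitivity" to other AAT products. Section 8.1.2 then closes the matter: "These reactions are not expected in this study because of the immunosuppressive nature of the transplant procedure".

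Other provisions that bear on the point:
- 6.1.3 fixes the eligibility review at days 4-7 after transplant, and at days 11-14 for patients screened again. The only screening chemistries in 6.1.6 are liver tests.
- 5.8 lets the investigator withdraw a patient for safety reasons, and 5.8.4 covers a condition that raises the participant's risk.
- 5.9 replaces patients who enrol but are never treated.
- 9.1 requires close monitoring during infusion, slowing or interruption if a reaction occurs, and 30 minutes of observation afterwards.

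**The concern.** The protocol names a group at raised risk of anaphylaxis from the study drug and then leaves that group out of the rules that decide who receives it. The drug is given pre-emptively, to patients who do not yet have acute GVHD (3.2.1), in 16 infusions over eight weeks (5.1.2). If a known, avoidable exposure is to be prevented, that has to happen before the first infusion. The monitoring in 9.1 limits harm only once exposure has begun. The numerical stopping rule in 8.7 counts grade 3 infections, so it would not register a hypersensitivity reaction.

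As written, five centers would each decide the question for themselves, and treatment must start within two days of a confirmed high-risk score (5.1). A criterion settled at the eligibility review avoids making that decision under time pressure. What is at stake is patient safety only.

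**Working it through.** The plan gives no figure to reproduce for this point. The check is a comparison of sections, followed by a small calculation of what the fix would cost.

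**1. Count the rules that mention IgA.**
- Inclusion criteria 3.1.1 to 3.1.11: 0 of 11.
- Exclusion criteria 3.2.1 to 3.2.9: 0 of 9.
- Together: 0 of 11 + 9 = 20. The synopsis has the same counts.
- Contraindications in 8.1.1: 0 of 1.
- Sections that state the hazard: 2 (8.1.2 and 9.1).

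**2. Follow one patient through the plan.** Take a patient with a high MAGIC score, antibodies to IgA on record, and no prior reaction to AAT.
- No inclusion criterion is failed on this account, and 3.2.9 is not met because there has been no reaction.
- The 8.1.1 contraindication does not apply, for the same reason.
- The registrar in Section 4.0 reviews the submitted eligibility documents. On the criteria as written, nothing flags this patient.
- The patient can be enrolled, and under 3.0 enrolment opens the way to dosing: "Study treatment may not begin until a subject is enrolled".

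A patient with the same antibodies who has already reacted to AAT is excluded by 3.2.9. The gap is therefore limited to those without such a reaction.

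**3. Identify what could still stop the first dose.** Section 3.0 sets conditions for eligibility but does not oblige a site to enrol every eligible patient, so a site can decline. After enrolment, 5.8 and 5.8.4 permit withdrawal. Both routes allow the dose to be withheld; neither requires it. Section 5.9 confers no discretion. It only replaces a patient who was never treated.

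**4. Test the reason given in 8.1.2.** The warning there names two groups: IgA-deficient patients with antibodies to IgA, and patients with prior hypersensitivity to other AAT products. The reassuring sentence covers both.
- Prior AAT allergy: excluded (3.2.9) and contraindicated (8.1.1).
- Antibodies to IgA: neither.

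The reason is not treated as sufficient for one group and is the only answer for the other. No data or citation accompanies it, and the difference is not explained.

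**5. Cost of an exclusion.** The inputs are from 11.2: about 120 eligible patients screened to enrol 30; more than 600 transplants a year, over 90% of them eligible; accrual within one year.
- Screens per enrolment: 120 / 30 = 4.
- If all eligible patients are screened: 600 × 0.90 = 540 a year, so 4 / 540 × 365 = 2.7 days.
- If only the planned 120 are screened over one year: 4 / 120 × 365 = 12.2 days.
- Patients lost: assumed 0 to 1, because the documents give no prevalence. Added screening is then 0 to 4 patients.

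**The case against.** The strongest reply is that this is a deliberate choice. Section 8.1.2 names the hazard and gives a reason for not acting on it, and nothing in the documents shows that reason to be wrong. A reader might infer that the authors overlooked the hazard; the text does not support that. What stands against the choice is that it is unsupported by data and is not applied to the other group in the same warning.

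The different treatment of the two groups can be defended in part. Prior allergy is a demonstrated reaction to the drug, whereas antibodies to IgA are a risk marker for a component that may be present only in traces. Treating the former more strictly is reasonable. It does not explain why the latter, when already known, should have no rule at all, given that the protocol itself warns of severe reactions.

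Three further points stand. An informed investigator has the warnings to hand and would probably withhold the drug. The fix uses history, so patients with undetected antibodies stay eligible. And the Investigator's Brochure or prescribing information (8.1), the Eligibility form (4.0) and the consent document (8.3.3) cannot be seen here and may already carry the item. The gap in the protocol text is established; whether there is a gap in practice is not.

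**Conclusion.** The point holds in a limited form. The lists that decide eligibility admit a patient with known antibodies to IgA and no prior AAT reaction, and whether that patient is dosed rests on investigator judgment. The change should be made, because the harm named is severe and the remedy is one line.

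The size of the risk cannot be stated. The documents give no prevalence of these antibodies, no reaction rate, and no IgA content beyond a trace. The count of 0 of 20 criteria describes coverage, not risk, and the trial might never meet such a patient.

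Two stronger readings are tempting and should not be drawn. One is that the plan compels dosing of these patients; it does not, since a site may decline to enrol and 5.8 allows withdrawal. The other is that the omission weakens the trial's result; it has no bearing on the endpoint, the sample size or the analysis.

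**What to change.** - Add *known antibodies to IgA (with or without documented IgA deficiency)* as exclusion 3.2.10, as a synopsis exclusion, and to 8.1.1.
- Check it from history at the existing 6.1.3 review, with no new laboratory test. A positive answer makes the patient a screen failure under Section 4.0, which avoids enrolling and then replacing the patient under 5.9.
- Qualify the closing sentence of 8.1.2 so that it does not extend to patients with known antibodies to IgA.
- If the Eligibility form already contains the item, copy it into 3.2 so that the protocol and the form agree.

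The cost is one more eligibility item and the possible loss of a rare patient. On the assumption of 0 to 1 such patients, that means up to about 4 more patients screened, or roughly 3 to 12 days of accrual. The review precedes the two-day treatment window in 5.1 and does not threaten it.

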## 4.0 SUBJECT SCREENING AND REGISTRATION PROCEDURES

### Study Schema

[figure not shown]

Figure 3: Study Schema

To be eligible for this study, patients must have a high MAGIC GVHD risk score on day 7 or 14 post-HCT (see Appendix). Patients will be recruited from centers participating in the Mount Sinai Acute GVHD International Consortium (MAGIC) where the procedures for obtaining screening samples for biomarker scoring are already established.

The pre-screening process is outlined in Figure 3 above. Consented patients will be registered into the remote data entry system using a unique study number assigned by the MAGIC DCC. Five mL of serum will be collected from patients on day 7 post-HCT (+/- 1 day) and shipped priority overnight to the Mount Sinai GVHD laboratory for early AM arrival (**see MAGIC Sample Collection and Storage manual for shipping procedures**). Samples can be received Tuesday through Saturday. Once received in the laboratory, the GVHD biomarkers used to assign the MAGIC GVHD risk score will be measured by ELISA using standard technical procedures. Processing, measuring, and confirming the ELISA assay results take 4.5 hours (range 4-6 hours). Once the MAGIC GVHD risk score is confirmed by [name] (or [name] in [name] absence), the investigator at the participating center will be notified of the MAGIC score by telephone and written confirmation by email.

Patients who are low risk on day 7, who have not already developed GVHD requiring systemic treatment, and who meet the other eligibility criteria will be re-screened on day 14 (+/- 1 day). Patients who were low risk on day 7 but high risk on day 14 are also eligible for this study provided they have not already developed GVHD requiring systemic treatment. Only patients with confirmed high MAGIC GVHD risk scores will be eligible to enroll on the clinical trial.

Patient registration for this trial will be centrally managed by the MAGIC Data Coordinating Center of the Icahn School of Medicine at Mount Sinai as described below:

A potential study subject who has been screened for the trial and who has signed the Informed Consent document will be initially documented by the participating site on the Screening and Enrollment Log provided by the MAGIC Data Coordinating Center (DCC).

It is the responsibility of the local site investigator to confirm patient eligibility for the clinical trial. Confirmation of a high MAGIC GVHD risk score will be provided directly to the identified Primary Site contact from the participating site by [name], [name] or designee. All other eligibility criteria will be provided by the participating site. After patient eligibility has been determined, a copy of the completed Eligibility form will be submitted by the requesting site to the MAGIC Data Coordinating Center by email to [[contact]](mailto:[contact]) with local site investigator signature and supporting source documentation.

The MAGIC Coordinator, who acts as the registrar, will review the submitted documents and process the registration.

An email will be sent by the registrar to the requesting site registrar to confirm patient registration. Patients found to be ineligible for participation after being consented will be considered screen failures, and documented as such in the Screening and Enrollment Log. These patients will not receive study treatment.

## 5.0 TREATMENT PLAN

### 5.1 Treatment Dosage and Administration

Protocol treatment must start within **2 days of confirmation of a high MAGIC GVHD risk score**. For example, a patient whose Day 7 post-HCT falls on a Friday (day 7), who has a research sample shipped to the [name] Lab that day, will have their MAGIC GVHD risk

score assigned on Saturday (day 8). Such a patient **must** begin study treatment no later than Monday (day 10). **There are no exceptions to this requirement.**

- 5.1.1 Alpha-1-antitrypsin (Glassia) will be supplied by Kamada. Each participating site will have a sufficient supply of alpha-1-antitrypsin on hand to begin treatment, additional doses will be shipped to the participating site to complete treatment. See section 9.1 for preparation, dispensing, and administration information.
- 5.1.2 Study treatment will consist of alpha-1-anti-trypsin administered intravenously at a loading dose of 90 mg/kg (study day 0) followed by twice weekly doses of 45 mg/kg for 15 more doses (total of 16 doses over 8 weeks).
- 5.1.3 The *planned* schedule of subsequent doses (Mondays and Thursdays, Tuesdays and Fridays, Wednesdays and Saturdays) can be adjusted as necessary so long as the time between doses is not shorter than two days or longer than four days.
- 5.1.4 Missed doses will be made up as soon as possible and the schedule resumed until all sixteen doses have been administered or ten weeks from first dose, whichever comes first.
- 5.1.5 Subjects who miss more than two doses due to non-compliance will be analyzed for safety but considered inevaluable for efficacy assessment and replaced.
- 5.1.6 **GVHD Prophylaxis Medications**  
Medications given for GVHD prophylaxis such as cyclosporine, tacrolimus, sirolimus, methotrexate, mycophenolate should be continued at therapeutic doses (according to institutional standards) and adjusted as necessary for renal, central nervous system (CNS) or other toxicity using institutional guidelines. This study allows for changes in GVHD prophylaxis medication (e.g., replacement of cyclosporine with sirolimus for management of posterior reversible encephalopathy syndrome [PRES]) as per institutional standards. The initiation of medications other than AAT for the purpose of intensifying GVHD prophylaxis in high risk patients is prohibited. GVHD prophylaxis medications will be tapered according to local institutional tapering practices.
- 5.1.7 **GVHD treatment**  
The preliminary data for this study was generated from patients transplanted at multiple centers with heterogeneous GVHD treatment practices. In order to develop “real world” experience in this study, institutional GVHD treatment practices are permitted unless their use is explicitly prohibited.  
  
Patients who develop GVHD will be treated as per institutional standards with systemic and non-systemic treatments such as topical steroids or non-absorbable steroids for GI GVHD. If systemic steroid treatment is initiated the recommended starting dose is **prednisone 2 mg/kg/day**. Centers may use a starting dose of 2 mg/kg of methylprednisolone if that is their institutional practice. Additional agents for the purpose of treating GVHD (e.g., etanercept, extracorporeal photopheresis, ATG) are not allowed. The initiation of systemic GVHD treatment beyond continuation or adjustment of GVHD prophylaxis medications (see section 5.1.6) and corticosteroids will be considered the initiation of second line GVHD treatment and considered a treatment failure. **Study treatment with alpha-1-antitrypsin continues during GVHD treatment until all 16 doses have been administered or ten weeks have elapsed from the start of AAT, whichever comes first.**

GVHD treatment will be tapered according to local institutional tapering practices. A recommended taper is provided in the appendices.

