### 5.5 Duration of Therapy

The duration of protocol therapy on this study is eight weeks (16 doses). Protocol therapy will end after the 16th dose of alpha-1-antitrypsin has been administered or if any of the following criteria apply:

- Patient voluntarily withdraws from treatment **OR**
- General or specific changes in the patient's condition render the patient unacceptable for further treatment in the judgment of the investigator **OR**
- Ten weeks has elapsed since the first dose of AAT

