### 5.6 Off Treatment Criteria

Patients will be removed from receiving the investigational drug when any of the criteria listed in Section 5.5 apply. The reason for ending investigational drug therapy and the date

the patient was removed from treatment will be documented in the study record. All patients who discontinue treatment should comply with protocol specific follow-up procedures as outlined in Section 5.7. The only exception to this requirement is when a subject withdraws consent for all study procedures.

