### **5.8 Off Study Criteria**

**Patients can be taken off study at any time at their own request, or they may be withdrawn at the discretion of the investigator for safety, behavioral or administrative reasons. The reason(s) for discontinuation from study will be documented and may include:**

- 5.8.1 Patient withdraws consent (termination of treatment and follow-up);
- 5.8.2 Loss of ability to freely provide consent through imprisonment or involuntary incarceration for treatment;
- 5.8.3 Patient is unable to comply with protocol requirements;
- 5.8.4 The subject has any disorder or condition that in the investigator's judgment may impede the participant's participation in the study, pose increased risk to the participant, or confound the results of the study
- 5.8.5 Patient becomes pregnant (pregnancy to be reported along same timelines as a serious adverse event);
- 5.8.6 Termination of the study;
- 5.8.7 Patient completes protocol treatment and follow-up criteria.

The informed consent documents will emphasize the importance of collecting outcome data from individuals who choose to discontinue treatment during the study, and participants will be encouraged to provide this information whether or not they complete the anticipated course of study treatment.

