### **5.9 Patient Replacement**

Patients who enroll in the study but do not receive any study treatment will be replaced. Patients who initiate study treatment but miss more than two doses due to non-compliance will also be replaced. The number of patients and reason(s) for replacement will be recorded and will be used to assess the feasibility of the study design.

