## 7.3 **Safety/Tolerability**

Analyses will be performed for all patients having received at least one dose of study drug. The study will use the CTCAE version 4.0 for reporting of adverse events (<http://ctep.cancer.gov/reporting/ctc.html>).

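### Treated patients who miss more than two doses through undefined non-compliance leave the efficacy count and are replaced, with no all-treated efficacy analysis planned beside the 6-of-30 rule

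*Combined protocol and SAP*

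**What the plan says.** Section 5.1.5: "Subjects who miss more than two doses due to non-compliance will be analyzed for safety but considered inevaluable for efficacy assessment and replaced". Section 5.9 confirms that this reaches patients already on drug: "Patients who initiate study treatment but miss more than two doses due to non-compliance will also be replaced". It adds that the number of replacements and the reasons are recorded, for the purpose of judging feasibility.

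Neighbouring provisions bear on who is caught:

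- Section 5.1.4: "Missed doses will be made up as soon as possible and the schedule resumed until all sixteen doses have been administered", with a limit of ten weeks from the first dose. It does not say whether a made-up dose still counts as missed.
- Section 5.5 lists "Patient voluntarily withdraws from treatment" among the ways therapy ends. It does not say whether such a patient is non-compliant.
- Section 5.2 keeps patients who stop for a drug-related SAE in the efficacy analyses.
- Section 5.1.7 continues AAT during GVHD treatment.
- Section 5.6 keeps patients who stop treatment in follow-up: "The only exception to this requirement is when a subject withdraws consent for all study procedures". The closing paragraph of section 5.8 says outcome data will be sought from those who discontinue.

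On analysis sets, section 7.3 says "Analyses will be performed for all patients having received at least one dose of study drug", but under the safety and tolerability heading. Section 7.1.1, on evaluability for response, can be read as an analysis set or only as the time assessment starts. Section 11.3 compares the study patients with 28% and names no efficacy set. Section 11.2 gives the go rule.

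**The concern.** The go decision rests on one count in an open-label, single-arm trial. A treated patient can be taken out of that count and replaced on a ground that arises after treatment starts, is undefined, and turns on motive. Nobody is assigned to decide it.

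The decision can be made with the outcome in view. With a score reported the day after sampling, first doses fall on about day 7-11 or 14-18 after HCT, so the ten-week limit falls on about day 77-88. Section 1.1 puts median GVHD onset at about one month. Onset near day 30 plus 28 days of steroids gives SR status near day 58, or earlier if second-line treatment starts. GVHD, and sometimes SR status, can therefore be known when missed doses are classified.

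The comparator has no matching exclusion. Section 11.1 describes the historical controls as patients with a high MAGIC score, and no adherence condition is stated for the 28%. If exclusion is related to SR GVHD, the count shifts and no planned analysis would show it.

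**Working it through.** **Inputs from the documents.** N = 30, null rate 0.28, alternative 0.15, one-sided exact test with target level 0.23, go if X ≤ 6, false-positive rates up to 0.25 tolerated (all section 11.2); 16 doses, twice weekly, ten-week limit (section 5.1).

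**Assumed, because the documents do not give them.** The share excluded, q; the SR rate among those excluded, p; the chance m of missing a dosing slot through non-compliance, taken as independent across slots.

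**1. The plan's own figures.** P(X ≤ 6 | 30, 0.28) = 0.224 and P(X ≤ 6 | 30, 0.15) = 0.847. A cut-off of 5 gives alpha 0.116 and one of 7 gives 0.368, so 6 is the right cut-off and the stated 85% power reproduces.

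**2. Effect of exclusion when AAT does nothing.** If the all-treated rate is 0.28, the rate in the evaluable set is (0.28 − q·p)/(1 − q), and the false-go probability is P(X ≤ 6) at that rate.

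| q | p = 0.10 | p = 0.28 | p = 0.40 | p = 0.60 |
|---|---|---|---|---|
| 1/30 | 0.202 | 0.224 | 0.239 | 0.266 |
| 0.10 | 0.160 | 0.224 | 0.275 | 0.374 |

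Example: q = 0.10, p = 0.60 gives (0.28 − 0.06)/0.90 = 0.2444 and P(X ≤ 6) = 0.374. The false-go reaches 0.25 at an evaluable rate of 0.273, that is p of about 0.48 at q = 1/30, or about 0.34 at q = 0.10.

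**3. How many could be excluded.** Ten weeks of twice-weekly dosing gives about 20 slots. The first dose is always received, since this limb covers only patients who have started.

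- If a made-up dose still counts as missed, exclusion needs 3 or more misses before the remaining 15 doses are given: P(Bin(17, m) ≥ 3) = 0.4%, 5.0% and 23.8% for m = 2%, 5% and 10%.
- If it does not, exclusion needs 13 or fewer of 16 doses received, so 7 or more misses in 19 slots: P(Bin(19, m) ≥ 7) is at most 0.17%, reached at m = 10%.
- Voluntary stopping would add to either if it counts as non-compliance. Make-up doses do not help there.

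**4. Sensitivity of the decision.** With 6 cases in 30 evaluable patients the result is a go (one-sided p = 0.224). Adding back one replaced patient who was an SR case gives 7 of 31, p = P(X ≤ 7 | 31, 0.28) = 0.327.

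**The case against.** The strongest reply is that the rule catches almost nobody. It covers non-compliance only. The more natural reading is that a made-up dose is not missed, and then intermittent misses exclude at most 0.17% at a 10% miss rate. Even if every such patient were an SR case, the evaluable rate would be (0.28 − 0.0017)/0.9983 = 0.2788 and the false-go 0.228, against 0.224. Related-SAE discontinuations stay in, GVHD does not itself stop AAT, and voluntary withdrawal is listed separately in section 5.5, so it may well lie outside non-compliance. Replacement reasons are recorded, follow-up continues, site investigators review conduct monthly, and the coordinating centre monitors adherence. A pre-specified evaluable set is a defensible choice for a pilot run at alpha 0.23.

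Most of this stands. It makes a large effect unlikely and means an all-treated count could largely be rebuilt. It does not settle which reading of a missed dose applies, whether voluntary stopping counts, or which count would be reported. The monthly reviewers are site investigators in an open-label trial, and none of the oversight provisions assigns or blinds the evaluability decision.

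A reader might infer three stronger things that the documents do not support.

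- That the rule favours AAT. Excluded patients with a lower SR rate push the decision the other way.
- That investigators may drop patients from efficacy at will. The discretion in section 5.8 ("they may be withdrawn at the discretion of the investigator for safety, behavioral or administrative reasons") concerns leaving the study, not evaluability.
- That outcomes of replaced patients are lost. Section 5.8.3 does list "Patient is unable to comply with protocol requirements" as a reason to leave the study, but section 5.6 and the end of section 5.8 point to continued collection. How a missing day-100 outcome is counted is a separate question.

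**Conclusion.** The point holds as a gap in the analysis plan, not as a demonstrated bias. Treated patients leave the efficacy count on an undefined ground that can be judged with GVHD status known, and nothing in section 11.3 would reveal an effect on the go decision. The sample size, cut-off and stated power are correct.

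Size and direction are unknown. The range of 0.202 to 0.266 assumes 1 in 30 excluded, and 0.160 to 0.374 assumes 10%, both with SR rates of 10% to 60% among those excluded and a true rate of 28%. If exclusion is unrelated to outcome, the false-go stays at 0.224. The 10% case needs the strict reading of a missed dose, or appreciable voluntary stopping classed as non-compliance. The correction deserves making because it is cheap and the decision can turn on one patient.

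**What to change.** **Section 11.3.** Pre-specify the SR GVHD count, with an exact interval, in all patients who received any AAT, reported beside the evaluable-set result. Fix its cut-off in advance as the largest with exact alpha of 0.23 or less, and state which result governs if the two disagree.

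| N treated | Go if | Alpha | Power at 15% |
|---|---|---|---|
| 31 | ≤ 6 | 0.194 | 0.827 |
| 32 | ≤ 6 | 0.167 | 0.805 |
| 33 | ≤ 6 | 0.143 | 0.783 |
| 34 | ≤ 7 | 0.224 | 0.873 |

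**Sections 5.1.5 and 5.9.** Define the evaluable set by doses received within ten weeks. State whether a made-up dose, and doses not given after voluntary stopping, count as missed. Have evaluability decided without knowledge of GVHD outcome. The definition must be squared with section 5.2, which keeps related-SAE discontinuations in efficacy, and with section 11.3, which counts death as failure. Exceptions by reason bring judgment back, so the all-treated count is still needed. Align section 7.1.1 with whichever sets are named.

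**Acceptable alternative.** Apply the 6-of-30 rule to the first 30 treated patients and replace only those never treated. Alpha stays at 0.224. The primary question becomes the effect of starting AAT rather than of near-complete dosing, and the cost is dilution: if 1, 2 or 3 of the 30 are under-dosed and stay at 28% while the rest are at 15%, P(Bin(30 − k, 0.15) + Bin(k, 0.28) ≤ 6) gives power 0.831, 0.813 or 0.794 for k = 1, 2 or 3.

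Either route is a wording change with no added patients and no change to any dose or treatment rule.
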